## **8.4. Vital Signs**

Values at each scheduled visit, change, and percent change from baseline for vital signs, including systolic blood pressure, diastolic blood pressure, pulse, respiratory rate, body weight, and body temperature will be summarized descriptively.

Criteria for clinically notable vital sign abnormalities are defined in Table 2. The abnormal values for subjects exhibiting clinically notable vital sign abnormalities will be listed. Alert vital signs are defined as an absolute value outside the defined range and percentage change from baseline greater than 25%. The abnormal values for subjects exhibiting alert vital sign abnormalities will also be listed.

**Table 2: Criteria for Clinically Notable Vital Sign Abnormalities**

| Parameter                | High Threshold | Low Threshold |
|--------------------------|----------------|---------------|
| Systolic blood pressure  | > 155 mmHg     | < 85 mmHg     |
| Diastolic blood pressure | > 100 mmHg     | < 40 mmHg     |
| Pulse                    | > 100 bpm      | < 45 bpm      |
| Temperature              | > 38°C         | < 35.5°C      |
| Respiratory rate         | > 24/min       | < 8/min       |

### 8.5. Electrocardiograms

Twelve-lead ECGs including PR, QRS, QT, and QTcF intervals, as well as heart rate, will be obtained for each subject during the study. Values at each scheduled visit, change, and percent change from baseline will be summarized for each ECG parameter. Change and percent change from baseline will be calculated using the average of all nonmissing values before the first administration of INCB054828 as the baseline value.

Criteria for clinically notable ECG abnormalities are defined in [Table 3](#). The abnormal values for subjects exhibiting clinically notable ECG abnormalities will be listed with study visit. Alert ECG values are defined as both the absolute value outside the defined range and the percentage change greater than 25% (QRS 30%). The abnormal values for subjects exhibiting alert ECG abnormalities will be identified and listed.

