3.2. Subject Exclusion Criteria

A subject who meets any of the following criteria will be excluded from the study:

1. Treatment with other investigational study drug for any indication for any reason, or receipt of anticancer medications within 28 days before first dose of study drug. Subjects must have recovered (Grade ≤ 1 or at pretreatment baseline) from AEs from previously administered therapies.
2. Untreated brain or central nervous system (CNS) metastases or brain/CNS metastases that have progressed (eg, evidence of new or enlarging brain metastasis or new neurological symptoms attributable to brain/CNS metastases). Subjects with previously treated and clinically stable brain/CNS metastases and who are off all corticosteroids for ≥ 4 weeks are eligible.
3. Known additional malignancy that is progressing or requires active treatment (ie, treatment administered within 3 years). Exceptions include basal cell carcinoma of the skin, squamous cell carcinoma of the skin, carcinoma in situ of the cervix, or other noninvasive or indolent malignancy that has undergone potentially curative therapy.
4. Are pregnant or lactating.
5. Prior receipt of a selective FGFR inhibitor.
6. Abnormal laboratory parameters:
 - a. Total bilirubin $\geq 1.5 \times$ upper limit of normal (ULN; $\geq 2.5 \times$ ULN if Gilbert syndrome or metastatic disease involving liver).
 - b. AST and ALT $> 2.5 \times$ ULN (AST and ALT $> 5 \times$ ULN in the presence of liver metastases).
 - c. Creatinine clearance ≤ 30 mL/min based on Cockcroft-Gault.
 - d. Serum phosphate $>$ institutional ULN.
 - e. Serum calcium outside of the institutional normal range or serum albumin-corrected calcium outside of the institutional normal range when serum albumin is outside of the institutional normal range.
7. History of calcium and phosphate homeostasis disorder.
8. History of human immunodeficiency virus infection.

9. Evidence of hepatitis B virus (HBV) or hepatitis C virus (HCV) active infection or risk of reactivation.
10. History or presence of an abnormal ECG that in the investigator's opinion is clinically meaningful. A screening QTcF interval > 450 milliseconds is excluded.

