5.4.5. Criteria for Permanent Discontinuation of Study Drug

The occurrence of unacceptable toxicity not caused by the underlying malignancy will be presumed to be related to study drug treatment and will require that the study drug be permanently discontinued. Unacceptable toxicity is defined as follows:

- Occurrence of an AE that is related to treatment with the study drug that, in the judgment of the investigator or the sponsor's medical monitor, compromises the subject's ability to continue study-specific procedures or is considered to not be in the subject's best interest.
- An AE requiring more than 2 dose reductions (unless dose has been up-titrated, then 3 dose reductions are allowed).
- Persistent AE requiring a delay of therapy for more than 21 days unless a greater delay has been approved by the sponsor.
- Increase in QT/QTcF to > 500 milliseconds or to > 60 milliseconds over baseline.

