9.4.2.4. Electrocardiograms

Descriptive statistics and mean change from baseline will be determined for each ECG parameter at each assessment time. Electrocardiogram results will be reviewed for clinically notable abnormalities according to predefined criteria ([Table 10](#)). Subjects exhibiting clinically notable ECG abnormalities will be listed.

Table 10: Criteria for Clinically Notable Electrocardiogram Abnormalities

Parameter	High Threshold	Low Threshold
QTcF	> 450 ms	< 295 ms
PR	> 220 ms	< 75 ms
QRS	> 120 ms	< 50 ms
QT	> 500 ms	< 300 ms
RR	> 1330 ms	< 600 ms

QTcF = Fridericia correction.

Data will be analyzed and presented using summary statistics.

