**Table 3: Criteria for Clinically Notable Electrocardiogram Abnormalities**

| Parameter | High Threshold | Low Threshold |
|-----------|----------------|---------------|
| QTcF      | > 460 msec     | < 295 msec    |
| PR        | > 220 msec     | < 75 msec     |
| QRS       | > 120 msec     | < 50 msec     |
| QT        | > 500 msec     | < 300 msec    |

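### SAP Table 3 flags QTcF only above 460 msec where Protocol Table 10 says 450 ms, with no change declared; separately, no SAP flag uses absolute rise over baseline

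*SAP*

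**What the plan says.** Protocol section 9.4.2.4 reviews ECG results against a table of limits ("Table 10: Criteria for Clinically Notable Electrocardiogram Abnormalities") and commits to an output: "Subjects exhibiting clinically notable ECG abnormalities will be listed". In that table the QTcF high limit is > 450 ms. The same figure is the entry limit in exclusion criterion 10: "A screening QTcF interval > 450 milliseconds is excluded".

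SAP section 8.5 makes the matching commitment: "The abnormal values for subjects exhibiting clinically notable ECG abnormalities will be listed with study visit". Its Table 3 has the same title, "Criteria for Clinically Notable Electrocardiogram Abnormalities", but its QTcF high limit is > 460 msec. The section then adds a second tier: "Alert ECG values are defined as both the absolute value outside the defined range and the percentage change greater than 25% (QRS 30" (the closing figure is a percentage). ECG change is measured "using the average of all nonmissing values before the first administration of INCB054828 as the baseline value".

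SAP section 10.1, which is the place for departures from protocol-defined analyses, says that none apply. The SAP's own change list in section 10.2.1 does not mention ECG limits.

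Protocol section 5.4.5 includes this among its criteria for unacceptable toxicity: "Increase in QT/QTcF to > 500 milliseconds or to > 60 milliseconds over baseline".

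**The concern.** Two documents that govern the same safety listing give different limits for the ECG interval of most interest, and nothing records that the difference was intended. A programmer who follows the SAP will produce a shorter listing than the protocol promises. Because subjects screened above 450 ms are excluded, an on-treatment value just above 450 ms is usually a new crossing of the protocol's limit.

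There is also a question of what the abnormality listings can show. The protocol names a rise of more than 60 ms over baseline as a QT/QTcF criterion. A reader of the study report would reasonably look in the abnormal and alert ECG listings for subjects who met it, but neither listing is built on absolute change. At stake is the completeness of a pre-specified safety display. No endpoint or estimate is affected.

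**Working it through.** There is no plan figure to reproduce; the check applies the stated limits.

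**Step 1: compare the tables** (Protocol Table 10 against SAP Table 3).

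| Parameter | Protocol | SAP |
|---|---|---|
| QTcF | > 450 / < 295 ms | > 460 / < 295 msec |
| PR | > 220 / < 75 ms | > 220 / < 75 msec |
| QRS | > 120 / < 50 ms | > 120 / < 50 msec |
| QT | > 500 / < 300 ms | > 500 / < 300 msec |
| RR | > 1330 / < 600 ms | no row |

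The QTcF high limit is the only shared limit that differs. Values above 450 and up to 460 ms are notable under the protocol and not under the SAP.

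**Step 2: write the SAP flags as rules.** Let b be baseline QTcF and v an on-treatment value, both in ms.

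- Notable: v > 460 or v < 295.
- Alert: notable, and |v − b| / b > 25%.

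Every alert is notable by definition. A QTcF value is therefore in neither listing exactly when 295 ≤ v ≤ 460, whatever the percentage change.

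**Step 3: find where a rise of more than 60 ms goes unlisted.** This needs v > b + 60 and v ≤ limit, which is possible only if b + 60 < limit.

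- SAP limit: b < 460 − 60 = 400 ms.
- Protocol limit: b < 450 − 60 = 390 ms.

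A search over whole-number baselines from 295 ms (an assumed lower end) to 450 ms (the entry limit) agrees. Unlisted cases exist for baselines of 295 to 399 ms under the SAP limit, and 295 to 389 ms under the protocol limit.

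**Step 4: examples.**

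| Baseline → value | Rise | % change | Notable, SAP | Alert, SAP | Notable, protocol |
|---|---|---|---|---|---|
| 390 → 455 | +65 | 65/390 = 16.7% | no | no | yes |
| 395 → 458 | +63 | 63/395 = 15.9% | no | no | yes |
| 385 → 446 | +61 | 61/385 = 15.8% | no | no | no |
| 360 → 455 | +95 | 95/360 = 26.4% | no | no | yes |
| 430 → 505 | +75 | 75/430 = 17.4% | yes | no | yes |
| 400 → 505 | +105 | 105/400 = 26.3% | yes | yes | yes |

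The 385 → 446 row shows that aligning the limit to 450 ms does not close the gap. The 360 → 455 row passes the 25% test and is still unlisted, so the percentage rule is not the cause.

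**Step 5: size of the 25% rule for QTcF.** A 25% change equals 60 ms only at b = 60 / 0.25 = 240 ms. At 390, 400 and 450 ms it requires rises above 97.5, 100 and 112.5 ms. The rule thus affects which notable values are also called alerts, but not which values go unlisted.

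**The case against.** The best counter-argument is that these are descriptive flags in a study whose SAP (section 3.1) calls all analyses exploratory, and that the data are not lost. Much of this stands. Listing 2.10.1 carries the 12-lead ECG values, and section 8.5 summarises change from baseline. Table 3.5.6 covers QT and QTc outliers, though its cut-offs are not stated, so it may or may not include > 60 ms. A discontinuation reported as an adverse event would appear in Listing 2.7.4.

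It is also fair that section 5.4.5 governs treatment. Protocol section 7.5.4 has investigators interpret ECGs for immediate subject management, and no document says the alert listing must identify subjects who meet 5.4.5. The > 60 ms flag is therefore a useful addition, not the repair of a broken commitment.

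A reader might infer three stronger things, and the documents support none of them.

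- That the SAP's alert rule is looser than the protocol's. The protocol defines alert values for vital signs only (section 9.4.2.3), so the ECG alert tier is an extra with no protocol counterpart.
- That the alert listing can never capture a subject who meets section 5.4.5. The 400 to 505 ms case is captured.
- That values above 500 ms escape. All of them exceed 460 ms and reach the notable listing; some, such as 430 to 505 ms, simply are not alerts.

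The missing RR row matters little. Limits of 600 and 1330 ms correspond to 60,000/600 = 100 and 60,000/1330 ≈ 45 bpm, which are the pulse limits in SAP Table 2.

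None of this explains the 450/460 difference, which the SAP leaves undeclared.

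**Conclusion.** The mismatch is real. Under the SAP, QTcF values above 450 and up to 460 ms are omitted from Listing 2.10.2 although the protocol says they will be listed. They remain, unflagged, in Listing 2.10.1. It is a modest reporting error.

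The second finding is separate and mostly not caused by the mismatch. Because neither flag uses absolute change, a rise above 60 ms can be in neither abnormality listing for any baseline below 400 ms, and for any below 390 ms even at the protocol's limit. How many subjects this would affect cannot be judged from the documents.

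The conclusion assumes that Listings 2.10.2 and 2.10.3 implement the notable and alert rules of section 8.5, as their titles indicate. It also assumes that the protocol limit was in force when the SAP was written. The SAP is based on Protocol Amendment 6 and the protocol at hand is Amendment 7. The Amendment 7 summary of changes names no ECG threshold change, but the Amendment 6 text is not available to confirm this. SAP section 2.1 states that the SAP applies to later amendments unless superseded.

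**What to change.** 1. Reconcile SAP Table 3 with Protocol Table 10 by setting the QTcF high reporting limit to > 450 msec. If > 460 msec was intended, declare and justify it in SAP section 10.1.
2. For reporting only, flag QTcF change > 60 ms over baseline and QTcF > 500 ms in Listing 2.10.3 or Table 3.5.6, using the quantities already in Protocol section 5.4.5. Say that the baseline is the pre-dose average defined in SAP section 8.5, and state the cut-offs for Table 3.5.6. Step 1 alone does not close the > 60 ms gap.
3. Restoring the RR row is optional.

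The cost is one table cell, one programming rule and slightly longer listings. No clinical rule changes.

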**Table 3: Criteria for Clinically Notable Electrocardiogram Abnormalities**

| Parameter | High Threshold | Low Threshold |
|-----------|----------------|---------------|
| QTcF      | > 460 msec     | < 295 msec    |
| PR        | > 220 msec     | < 75 msec     |
| QRS       | > 120 msec     | < 50 msec     |
| QT        | > 500 msec     | < 300 msec    |

## 9. INTERIM ANALYSES

A futility analysis will be performed when approximately 45 subjects with FGFR3 mutations or fusions who have been treated and have had at least 1 tumor assessment or have permanently discontinued study treatment in Cohort A-ID. The study will be stopped for futility if 10 or fewer responders are observed, for which there is less than 15% probability of claiming ORR > 25% at final analysis.

## 10. CHANGES AND MODIFICATIONS TO THE ANALYSIS PLAN

All versions of the SAP are listed in [Table 4](#).

**Table 4: Statistical Analysis Plan Versions**

| SAP Version | Date        |
|-------------|-------------|
| Original    | 16 MAY 2017 |
| Amendment 1 | 12 JUN 2019 |

### 10.1. Changes to Protocol-Defined Analyses

Not applicable.

### 10.2. Changes to the Statistical Analysis Plan

#### 10.2.1. Original to Amendment 1

The original SAP has been updated to incorporate Protocol Amendments 4, 5, and 6. Specific changes are outlined below:

- Moved analysis of largest percentage reduction in sum of diameters of target lesions from Section 7.3, Analysis of the Secondary Efficacy Parameters to Section 7.4, Other Efficacy Analyses.
- Summaries of prior cisplatin use and prior immune therapy have been added.
- Average daily dose has been updated to use duration of treatment as the denominator.
- Investigator-assessed efficacy parameters have been added as other efficacy analyses.
- Summary of weight has been moved from efficacy section to vital sign section.

## APPENDIX A. PLANNED TABLES, FIGURES, AND LISTINGS

This appendix provides a list of the planned tables, figures, and listings for the CSR. Standard tables will follow the conventions in the Standard Safety Tables initial version. Shells are provided for nonstandard tables. In-text tables are identical in structure and content as appendix tables, but follow a Rich Text Format.

The list of tables, figures, and listings and the shells are to be used as guidelines. Modifications of the lists or shells that do not otherwise affect the nature of the analysis will not warrant an amendment to the SAP.

### Tables

| Table No.                                       | Title   | Population   |
|---|---|--------------|
| Baseline and Demographic Characteristics |   |              |
| 1.1.1   | Analysis Populations  | All Enrolled |
| 1.1.2   | Summary of Subject Disposition  | Efficacy     |
| 1.1.3   | Summary of Number of Subjects Enrolled by Country and Site  | Efficacy     |
| 1.1.4   | Summary of Protocol Deviations  | Efficacy     |
| 1.2.1   | Summary of Demographics and Baseline Characteristics  | Efficacy     |
| 1.2.2   | Summary of Disease History  | Efficacy     |
| 1.2.3   | Summary of Prior Systemic Cancer Therapy  | Efficacy     |
| 1.3   | Summary of General Medical History  | Efficacy     |
| 1.4.1   | Summary of Prior Medications  | Efficacy     |
| 1.4.2   | Summary of Concomitant Medications  | Efficacy     |
| Efficacy                                 |   |              |
| 2.1.1   | Summary of Best Response and Overall Response Rate  | Efficacy     |
| 2.1.2   | Summary of Best Response and Overall Response Rate  | Per Protocol |
| 2.2.1   | Summary of Duration of Response   | Efficacy     |
| 2.2.2   | Summary of Progression-Free Survival  | Efficacy     |
| 2.2.3   | Summary of Overall Survival   | Efficacy     |
| 2.2.4   | Summary of Best Change in Target Lesion Size  | Efficacy     |
| 2.3.1   | Summary of ECOG Performance Status  | Efficacy     |
| Safety                                   |   |              |
| 3.1.1   | Summary of Study Drug Exposure  | Safety       |
| 3.1.2   | Summary of Study Drug Compliance  | Safety       |
| 3.2.1   | Overall Summary of Treatment-Emergent Adverse Events  | Safety       |
| 3.2.2   | Summary of Treatment-Emergent Adverse Events by MedDRA System Organ Class and Preferred Term                    | Safety       |
| 3.2.3   | Summary of Treatment-Emergent Adverse Events by MedDRA Preferred Term in Decreasing Order of Frequency          | Safety       |
| 3.2.4   | Summary of Treatment-Emergent Adverse Events by MedDRA System Organ Class, Preferred Term, and Maximum Severity | Safety       |
| 3.2.5   | Summary of Treatment-Emergent Grade 3 or Higher Adverse Events by MedDRA System Organ Class and Preferred Term  | Safety       |

| Table No.  | Title  | Population |
|-------------------|---|-------------------|
| 3.2.6             | Summary of Treatment-Emergent Grade 3 or Higher Adverse Events by MedDRA Preferred Term in Decreasing Order of Frequency                    | Safety            |
| 3.2.7             | Summary of Treatment-Related Adverse Events by MedDRA System Organ Class and Preferred Term   | Safety            |
| 3.2.8             | Summary of Treatment-Related Adverse Events by MedDRA Preferred Term in Decreasing Order of Frequency                                       | Safety            |
| 3.2.9             | Summary of Treatment-Related Grade 3 or Higher Adverse Events by MedDRA System Organ Class and Preferred Term                               | Safety            |
| 3.2.10            | Summary of Treatment-Emergent Adverse Events With a Fatal Outcome by MedDRA System Organ Class and Preferred Term                           | Safety            |
| 3.2.11            | Summary of Treatment-Emergent Serious Adverse Events by MedDRA System Organ Class and Preferred Term  | Safety            |
| 3.2.12            | Summary of Treatment-Emergent Serious Adverse Events by MedDRA Preferred Term in Decreasing Order of Frequency                              | Safety            |
| 3.2.13            | Summary of INCB054828 Treatment-Related Serious Adverse Events by MedDRA System Organ Class and Preferred Term                              | Safety            |
| 3.2.14            | Summary of Treatment-Emergent Adverse Events Leading to INCB054828 Dose Interruption by MedDRA System Organ Class and Preferred Term        | Safety            |
| 3.2.15            | Summary of Treatment-Emergent Adverse Events Leading to INCB054828 Dose Reduction by MedDRA System Organ Class and Preferred Term           | Safety            |
| 3.2.16            | Summary of Treatment-Emergent Adverse Events Leading to Discontinuation of INCB054828 by MedDRA System Organ Class and Preferred Term       | Safety            |
| 3.2.17            | Summary of Treatment-Emergent Adverse Events and Grade 3 or Higher Adverse Events by MedDRA Preferred Term in Decreasing Order of Frequency | Safety            |
| 3.2.18            | Summary of Treatment-Emergent Non-Serious Adverse Events by MedDRA System Organ Class and Preferred Term                                    | Safety            |
| Laboratory |   |                   |
| 3.3.1             | Summary of Laboratory Values - Hematology   | Safety            |
| 3.3.2             | Shift Summary of Hematology Values in CTC Grade - To the Worst Abnormal Value   | Safety            |
| 3.3.3             | Summary of Treatment-Emergent Worsening of Laboratory Abnormalities - Hematology  |                   |
| 3.3.4             | Summary of Laboratory Values - Chemistry  | Safety            |
| 3.3.5             | Shift Summary of Chemistry Values in CTC Grade - To the Worst Abnormal Value  | Safety            |
| 3.3.6             | Summary of Treatment-Emergent Worsening of Laboratory Abnormalities - Chemistry   |                   |
| 3.3.7             | Summary of Laboratory Values - Coagulation  | Safety            |
| 3.3.8             | Shift Summary of Coagulation Values in CTC Grade - To the Worst Abnormal Value  | Safety            |
| 3.3.9             | Summary of Treatment-Emergent Worsening of Laboratory Abnormalities - Coagulation   | Safety            |
| 3.3.10            | Summary of Laboratory Values - Urinalysis   | Safety            |

| Table No.   | Title   | Population |
|--------------------|--|-------------------|
| Vital Signs |  |                   |
| 3.4.1              | Summary of Systolic Blood Pressure                                 | Safety            |
| 3.4.2              | Summary of Diastolic Blood Pressure                                | Safety            |
| 3.4.3              | Summary of Pulse   | Safety            |
| 3.4.4              | Summary of Body Temperature  | Safety            |
| 3.4.5              | Summary of Respiratory Rate  | Safety            |
| 3.4.6              | Summary of Body Weight   | Safety            |
| ECG         |  |                   |
| 3.5.1              | Summary of PR Interval (ms) From 12-Lead ECG                       | Safety            |
| 3.5.2              | Summary of QRS Interval (ms) From 12-Lead ECG                      | Safety            |
| 3.5.3              | Summary of QT Interval (ms) From 12-Lead ECG                       | Safety            |
| 3.5.4              | Summary of QTc Interval (ms) From 12-Lead ECG                      | Safety            |
| 3.5.5              | Summary of Heart Rate (bpm) From 12-Lead ECG                       | Safety            |
| 3.5.6              | Summary of Outliers of QT and QTc Interval Values From 12-Lead ECG | Safety            |
| 3.5.7              | Summary of Clinically Significant ECG Abnormalities                | Safety            |

